4.9.4 PDAI data

PDAI skin activity score (0-120), mucous membrane activity score (0-120), scalp activity score (0-10), skin damage score (0-12), scalp damage score (0-1), total activity score (0-250), and total damage score (0-13) will be summarized by cohort and visit. Higher score indicates higher impact of skin disease. Descriptive statistics will include absolute change from baseline, and percentage change from baseline.

PDAI total activity score ranges from 0 to 250. The number and percentage of subject will be summarized by disease severity category based on PDAI total activity score, such as mild (0-8), moderate (9-24), and severe (≥ 25).

4.10 Analysis of Exploratory Endpoints

4.10.1 Exploratory Pharmacodynamic/ Activity Analysis

Exploratory PD and disease activity markers will include:

- Complement component 3
- AECA
- FCGR2A
- RNAseq
- Immunophenotyping
- Urine IgG levels to explore SYNT001 distribution and elimination (Cohort 1 only)
- Exploratory Pemphigus Immune Response Biomarkers

All exploratory PD/disease activity data will be summarized by cohort and visit. Descriptive statistics will include mean, SD, median, minimum, and maximum. Mean (\pm SD) of values and percentage change and absolute change from baseline will also be plotted.

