2.3 Exploratory Objective and Endpoint

Exploratory Objectives	Exploratory Endpoints
To explore the effect of SYNT001 at different dose levels and dosing regimens on biomarkers to understand the pathophysiology of the disease and the SYNT001 mechanisms of action	
The exploration of SYNT001 mechanisms of action and effects of SYNT001 on pathophysiology summarized by dose, dosing regimen and visit as determined by:
 
 • Complement component 3 levels by nephelometry

Exploratory Objectives	Exploratory Endpoints
	
 • Anti-epithelial cell antibody (AECA) titers by indirect immunofluorescence • Fc gamma R2A receptor (FCGR2A) single nucleotide polymorphisms (SNP) by genotyping • Presence of disease and inflammatory markers by total RNA sequencing • Immunophenotyping including measurements of T cells, monocytes, natural killer (NK) cells and B cells by flow cytometry • Urine IgG levels to explore SYNT001 distribution and elimination (Cohort 1 only) • Exploratory biomarkers to investigate immune response associated with pemphigus
To determine the impact of different SYNT001 dose levels and dosing regimens on the subject's use of corticosteroids to treat their pemphigus (vulgaris or foliaceus)	The evaluation of corticosteroid use during the study will be summarized by dose, dosing regimen and visit
To assess the impact of SYNT001 on the subject's health-related quality of life (HR-QoL) at different dose levels and dosing regimens	The assessment of SYNT001 impact on subject's health-related quality of life (HR-QoL) by responses to the Autoimmune Bullous Diseases Quality of Life (ABQoL) questionnaire and Skindex-29 scores summarized by dose, dosing regimen and visit
To assess the effect of SYNT001 on the appearance of skin and mucosal lesions at different dose levels and dosing regimen	The qualitative assessment of changes in appearance of skin and mucosal lesions as determined by photography presented by dose, dosing regimen and visit
To quantify the amount of SYNT001 in skin (skin biopsies optional)	The determination of SYNT001 levels in skin biopsies across time points (skin biopsies optional) (Cohort 1 only)

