3. STUDY OVERVIEW

3.1 Overall Study Design and Treatment Assignment

This is a multicenter, open-label safety study to determine the dose regimen of SYNT001 administered IV in subjects with pemphigus (vulgaris or foliaceus). Up to 8 subjects with a

diagnosis of pemphigus (vulgaris or foliaceus) will receive SYNT001 10 mg/kg weekly x 5 doses (Cohort 1). Up to 12 subjects with a diagnosis of pemphigus (vulgaris or foliaceus) will receive SYNT001 30 mg/kg weekly x 3 doses (Loading), followed by SYNT001 10 mg/kg every other week x 5 doses (Maintenance) (Cohort 2).

Subjects in both cohorts will complete the following periods of assessment: Screening, Treatment, and Follow-Up.

The Dose Escalation Committee (DEC) will consist of the Medical Monitor, an Independent Clinical Expert and the Sponsor Medical Lead. The DEC may request that Investigators, other experts, or members within their organization participate in the review. Additional information on the DEC’s responsibilities is provided in Protocol Section 9.5 and the DEC Charter.

An overview of the study cohorts is provided in Table 1.

Table 1. Cohort Overview

Cohort No.	No. of subjects	SYNT001 Dose	No. of Doses	Frequency of Doses
1 ^a	Up to 8	10 mg/kg	5	NA
2 ^b	Up to 12	Loading: 30 mg/kg ^c Maintenance: 10 mg/kg ^c	3 ^c 5 ^c	Weekly ^c Every other week ^{c, d}

- a. No more than 3 subjects with pemphigus foliaceus may be enrolled
- b. Two or fewer subjects with pemphigus foliaceus may be enrolled
- c. The dose, number of doses, and frequency of doses in Cohort 2 will be confirmed based on review of safety and PD evaluations, including but not limited to, dose-limiting toxicities, AEs, TEAEs, SAEs, and total IgG levels. Following Sponsor review of emerging safety, PD and efficacy data, the Loading dose may be reduced to 20 or 10 mg/kg weekly and/or the Maintenance dose may be increased to 20 or 30 mg/kg every other week and/or dose frequency may be increased to weekly.
- d. Ongoing safety and PD evaluations may result in modification of the dose and dosing regimen in Cohort 2. See Protocol APPENDIX 5 for the corresponding visit schedule.

The duration of subject participation for each cohort is as follows:

Cohort	Screening	Treatment	Follow-up	Maximum Total	
				Days	Weeks
1	≤14 days	28 days	84 days	126 days	18 weeks
2	≤14 days	84 days	56 days	154 days	22 weeks

Subjects will be enrolled at staggered intervals to facilitate adequate safety evaluation before dosing of subsequent subjects.

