4.1 General Design

All clinical data captured will be provided in data listings. Subject disposition, demographic information, and baseline characteristics will be presented. Baseline will be defined as the last value obtained prior to the first dose of study drug. Results will be summarized by dose and dosing regimen (cohort), and in total. Any discrepancy between treatment to be given and treatment received will be accounted for in these displays.

Continuous data will be summarized using descriptive statistics: number of subjects (N), number of observations (n), mean, median, standard deviation (SD), minimum, and maximum.

Categorical data will be summarized using frequencies and percentages. When categorical data will be presented, the percent will be suppressed when the count is zero to draw attention to the non-zero counts. The denominator for all percentages, unless otherwise specified, will be the number of subjects in the specified analysis population.

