4.9 Analysis of Secondary Endpoints

4.9.1 Pharmacokinetic Analysis

PK results for SYNT001 will be summarized by cohort, visit and time point.

Descriptive statistics will be provided for the PK parameters including mean, SD, CV, median, minimum, and maximum.

For calculation of mean concentrations and generation of mean concentration-time profiles, all below the limit of quantification (BLQ) values will be set to zero except when an individual BLQ falls between 2 quantifiable values, in which case it will be omitted.

If there are values above the BLQ, but too sparse to allow full analysis, descriptive statistics will be performed on available values.

PK concentrations will be summarized descriptively at each nominal time point by cohort using n, mean, SD, percent coefficient of variation (CV%), standard error, median, minimum, maximum, geometric mean, geometric CV%.

Mean concentrations (\pm SD) of SYNT001 will be plotted on a linear and semi-logarithmic scale against nominal time points, by cohort. Individual concentration for each subject will be plotted using original scale and semi-log scale.

Study drug concentrations will be used to calculate the following PK parameters, if feasible:

Parameters	Description
C_{max}	Maximum observed plasma concentration observed directly from data
T_{max}	Time to reach maximum observed concentration directly from data
λ_z	Apparent first-order terminal elimination rate constant calculated by linear regression of the terminal linear portion of the log concentration vs. time curve
$t_{1/2}$	Terminal elimination half-life, calculated as $\ln(2)/\lambda_z$
AUC_{0-24}	AUC from time zero to 24 hours post-dose administration
$AUC_{0-\infty}$	AUC from time zero to infinity time (as $AUC_{0-t} + C_{last}/\lambda_z$, where C_{last} is the last quantifiable concentration)

Actual sampling time will be used for PK calculations. Actual sampling times that are outside the scheduled sampling times window described in [Table 4](#) will be excluded from summary statistics of PK concentrations but will still be used in the calculations of PK parameters.

The Linear Up Log Down method will be used in the computation of AUCs. The PK parameters λ_z and $t_{1/2}$ will not be presented for subjects who do not exhibit a terminal elimination phase in their concentration-time profiles.

The constant λ_z will not be assigned if one of the following happens:

1. T_{max} is or is equal to one of the 3 last data points,

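### AECA titers are averaged and plotted on the arithmetic scale, which tilts the mean percent change upward and lets one large riser set the sign of the plotted mean in cohorts of 8 or 12

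*SAP*

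**What the plan says.** Section 2.3 of the SAP lists the endpoint as "Anti-epithelial cell antibody (AECA) titers by indirect immunofluorescence". Section 4.10.1 names AECA among the exploratory markers and sets one rule for the whole list: "All exploratory PD/disease activity data will be summarized by cohort and visit". The statistics are fixed as well: "Descriptive statistics will include mean, SD, median, minimum, and maximum". For the figures, "Mean (\pm SD) of values and percentage change and absolute change from baseline will also be plotted".

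No log transformation, geometric mean or summary in dilution steps is given for AECA. The default for continuous data in section 4.1 does not supply one; it lists "number of subjects (N), number of observations (n), mean, median, standard deviation (SD), minimum, and maximum". Geometric statistics do appear in this SAP, but only for PK concentrations in section 4.9.1 ("maximum, geometric mean, geometric CV").

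Section 3.1 caps the cohorts at 8 subjects (Cohort 1) and 12 subjects (Cohort 2). Table 5 schedules AECA on Day 0 and five later visits in Cohort 1. In Cohort 2 it is scheduled at screening, on Day 0 and at ten later visits.

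**The concern.** A titer is read off a dilution series, so its natural steps are multiplicative. On a doubling series one step up is +100% and one step down is -50%. Equal and opposite movements therefore do not cancel in an arithmetic mean of percent changes; they leave a positive remainder. The mean absolute change has a related weakness, because the subject with the highest titer dominates it.

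The question for this marker is whether SYNT001 lowers the antibody. A mean that drifts upward under pure noise, and that one subject can turn round in a cohort of 8 or 12, answers it poorly. What is at stake is how the AECA mean columns and figures will be read in the study report. The figures matter most, because they carry nothing but mean ± SD.

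**Working it through.** The SAP gives no AECA figure to reproduce, and it states neither the dilution factor nor the assay noise. Both are assumptions here: a dilution factor f of 2 (range 2 to 4) and a probability p of 0.10 to 0.50 that a subject moves one step in each direction. Cohort sizes (8 and 12) are the maxima in section 3.1.

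**1. Noise only, no true change.** Expected mean percent change = 100 × [p(f − 1) + p(1/f − 1)].

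| f | p = 0.10 | p = 0.25 | p = 0.50 |
|---|---|---|---|
| 2 | +5.0% | +12.5% | +25.0% |
| 3 | +13.3% | +33.3% | +66.7% |
| 4 | +22.5% | +56.25% | +112.5% |

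For example, f = 2 and p = 0.25 gives 0.25 × 100 − 0.25 × 50 = +12.5%. The mean log2 change is zero in every cell, so the geometric mean ratio is 1.00. The direction follows from symmetry on the log scale alone; f and p set only the size.

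If the baseline reading carries the same noise (f = 2, p = 0.25), each reading contributes a factor 0.25 × 2 + 0.5 × 1 + 0.25 × 0.5 = 1.125. The expected change is then 1.125² − 1 = +26.6%.

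**2. The same noise at the planned cohort sizes** (f = 2, p = 0.25, noise in the change only, 200,000 simulated cohorts).

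- n = 8: the mean percent change is above zero in 67% of cohorts and below zero in 22%.
- n = 12: above zero in 74%, below zero in 18%.
- The mean log2 change is above zero in 40% (n = 8) and 42% (n = 12). By symmetry it is below zero equally often.

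**3. One riser against subjects who halve** (doubling steps). A rise of k steps adds 100 × (2^k − 1) percentage points to the sum, and each halving subject takes away 50.

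- One step (+100): outweighs 1 halving subject; 2 cancel it.
- Two steps (+300): outweighs up to 5 if the rest are unchanged; 6 cancel it. Five is a majority of 8 but not of 12.
- All n − 1 others halve: the break-even fold rise is 1 + 0.5(n − 1), which is 4.5 for n = 8 and 6.5 for n = 12. On a doubling series the first step beyond either is 8-fold.

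Examples:

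| Pattern | Mean % change | Median % change | Geometric mean change |
|---|---|---|---|
| n = 8: 5 halve, 2 unchanged, 1 rises 4-fold | (−250 + 300)/8 = +6.25% | −50% | 2^(−3/8) = 0.77, i.e. −23% |
| n = 8: 7 halve, 1 rises 8-fold | (−350 + 700)/8 = +43.75% | −50% | 2^(−4/8) = 0.71, i.e. −29% |
| n = 12: 11 halve, 1 rises 8-fold | (−550 + 700)/12 = +12.5% | −50% | 2^(−8/12) = 0.63, i.e. −37% |

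**4. Raw values behave the same way.** Let seven subjects go from 40 to 20 and one from 640 to 1280. The arithmetic mean rises from 115 to 177.5, while the geometric mean falls from 56.6 to 33.6 and the median from 40 to 20.

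**The case against.** The strongest reply is that section 4.10.1 also tabulates the median, minimum and maximum. In every reversal example above the median is −50%, and the maximum exposes the lone riser. Section 4 further promises listings of all captured clinical data, so with 8 or 12 subjects each titer can be read directly. This stands, and it confines the point to the mean columns and the plots. The median is not wholly immune to noise in small cohorts: in the simulation at p = 0.25 its average was +3.6% (n = 8) and +1.7% (n = 12). It is still much closer to zero than the mean.

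Second, nothing rests on AECA. It is exploratory and descriptive, and dose selection (sections 2.1 and 4.8) uses total IgG and PDAI. The noise effect also pushes toward an apparent rise, so by itself it would understate a fall and not create one. This stands and keeps the severity low.

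Third, the sizes depend on assumed inputs. That is true of the sizes, but not of the direction under log-symmetric noise.

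A reader might infer more: that the plan would conceal a fall in AECA, or that any one rising subject reverses the result. The documents do not support either. The median and range are reported, a one-step rise outweighs only one halving subject, and a two-step rise cannot overturn a halving majority of 12. A reader might also infer that the blanket rule would average the FCGR2A genotype. The categorical-data rule in section 4.1 can reasonably be read to cover it.

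**Conclusion.** The point holds in a limited form. For a marker that the SAP itself defines as a titer, the arithmetic mean and the mean ± SD plots of percent and absolute change are a poor choice. Under log-symmetric noise and doubling dilutions, the expected mean percent change with no true effect lies between +5% and +25% for the noise rates considered, and up to +112.5% with four-fold steps. Reversal by one subject is possible but conditional. It needs a rise of at least two doubling steps to outweigh five halving subjects, or more than 4.5-fold (n = 8) or 6.5-fold (n = 12) when everyone else halves.

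These sizes rest on an assumed dilution factor and noise rate and on full cohorts. Because robust statistics are tabulated alongside and no decision uses AECA, this is an improvement worth making, not a threat to any conclusion of the trial.

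**What to change.** In section 4.10.1, take AECA out of the common rule and specify, by cohort and visit:

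- geometric mean titer;
- geometric mean ratio to baseline, computed as 2 raised to the mean log2 change;
- median, minimum and maximum, as now;
- plots of geometric mean titer and geometric mean ratio in place of the arithmetic mean ± SD plots;
- one fixed value for titers below the lowest dilution, for example half the lowest dilution, stated before database lock.

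The cost is a small change to SAP wording and table and figure shells, with no new data. The geometric summary will depend to some degree on the below-limit value. Using half the lowest dilution instead of the lowest dilution moves one subject by one log2 unit. For each subject who falls below the limit from a measurable baseline, this multiplies the cohort ratio by 2^(−1/8) = 0.92 at n = 8 or 2^(−1/12) = 0.94 at n = 12. The number of below-limit results should therefore be shown beside the summary.

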4.10.2 Corticosteroid Use

The number and percent of subjects who use corticosteroid will be summarized by cohort and visit.

4.10.3 Health-Related Quality of Life Data

For Cohort 2, Autoimmune Bullous Disease Quality of Life (ABQOL) questionnaire total score will be calculated and summarized by visit.

SKINDEX-29 is a three-dimensional, dermatology-specific HRQL questionnaire. Twenty-nine items are combined to form three domains: symptoms, emotions, and functioning. The domain scores and an overall score are expressed on a 100-point scale, with higher scores indicating lower levels of quality of life.

Domains/Scales	Number of Items	Cluster of Items	Item reversion	Direction of Domains
Emotions	10	3; 6; 9; 12; 13; 15; 21; 23; 26; 28	No	Higher score = higher impact of skin disease
Symptoms	7	1; 7; 10; 16; 19; 24; 27		
Functioning	12	2; 4; 5; 8; 11; 14; 17; 20; 22; 25; 29; 30		

Note: Item 18 is a single item, not included in scoring.

All responses are transformed to a linear scale of 100. Transformed item scores: never = 0, rarely = 25, sometimes = 50, often = 75, and all the time = 100. A scale score is the mean of a patient’s responses to the items in a given scale. If responses to more than 25% of items are missing overall, the questionnaire is eliminated. If any scale has more than 25% of the responses missing, the scale is missing. Scale scores are the average of non-missing items in a given scale. An item with multiple answers is considered missing.

For Cohort 2, three domain scores and the overall score from SKINDEX-29 will be summarized by visit.

4.10.4 Photography

The quantitative photography data will not be part of the database. Only visit and date of collection will be listed in data listing. No summary table will be presented.

4.10.5 Skin Biopsy

The quantitative skin biopsy data will not be part of the database. Only visit, date of collection and type of skin will be listed in data listing. No summary table will be presented.

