3.1.19 Skin Biopsy

In Cohort 1, optional skin biopsy samples from lesional or non-lesional skin will be collected to analyze SYNT001 levels.

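### Section 4.10.5 plans no output showing SYNT001 levels in skin, although Section 2.3 makes those levels an exploratory endpoint; the photography wording in 4.10.4 also does not match 2.3

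*SAP*

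**What the plan says.** **Skin biopsy.** The exploratory objective in SAP Section 2.3 is "To quantify the amount of SYNT001 in skin (skin biopsies optional"), and its endpoint is "The determination of SYNT001 levels in skin biopsies across time points (skin biopsies optional) (Cohort 1 only"). Section 3.1.19 gives the purpose of the samples: in Cohort 1, "optional skin biopsy samples from lesional or non-lesional skin will be collected to analyze SYNT001 levels". Section 4.10.5 says "The quantitative skin biopsy data will not be part of the database" and "Only visit, date of collection and type of skin will be listed in data listing", with no summary table.

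**Photography.** The exploratory endpoint in Section 2.3 is "The qualitative assessment of changes in appearance of skin and mucosal lesions as determined by photography presented by dose, dosing regimen and visit". Section 4.10.4 says "The quantitative photography data will not be part of the database" and "Only visit and date of collection will be listed in data listing", again with no summary table.

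**General rules.** Section 1 makes the results of the SAP's analyses the basis of the clinical study report. It also allows further analyses, provided the report identifies them. Sections 4 and 4.1 say that all captured clinical data will be listed.

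**The concern.** An analysis section should say how each endpoint in the objectives table will be shown. For skin levels, Section 4.10.5 does the opposite: it excludes the one variable that constitutes the endpoint and keeps only the circumstances of collection. This is more than missing detail, because a stated rule defeats a stated endpoint. A programmer who follows the SAP would produce a listing of when biopsies were taken and from what kind of skin, with no concentration in it. The clinical study report would then carry an exploratory endpoint for which no result had been planned.

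The photography section raises a related but weaker question. The kind of data it names is not the kind that Section 2.3 promises, and the listing it plans contains no assessment.

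**Working it through.** No estimate, error rate or sample size enters this point, so the check is a comparison of sections.

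**Step 1: what each endpoint needs, and what is planned.**

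| | Skin biopsy | Photography |
|---|---|---|
| Kind of data in 2.3 | Quantitative: SYNT001 level | Qualitative: change in lesion appearance |
| Layout in 2.3 | Across time points, Cohort 1 only, optional | By dose, dosing regimen and visit |
| Kept out of the database (4.10.4, 4.10.5) | Quantitative biopsy data | Quantitative photography data |
| Listed | Visit, date, skin type | Visit, date |
| Summary table | None | None |
| Planned output with a result | None | None |

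For biopsy, the excluded data and the endpoint are the same thing. For photography they are not: the exclusion covers quantitative data, and the endpoint is qualitative. The photography gap comes only from the content of the listing.

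**Step 2: could the skin levels be reported under another section?**
- Section 4.9.1 summarises SYNT001 concentrations, but the PK notes to Tables 2 and 3 define these samples as serum, and the PK windows in Table 4 do not mention skin.
- Sections 4.9.2 and 4.10.1 and Table 5 list the pharmacodynamic and exploratory markers. Skin levels are not among them.
- Section 4.9.3 shows how the SAP handles results that may come late: it summarises the immunogenicity results available at database lock. Section 4.10.5 has no such provision.
- The rule in Sections 4 and 4.1 that captured clinical data are listed would cover skin levels only if they count as captured. Section 4.10.5 suggests that they do not, so this rule gives no firm answer.

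No section of the SAP supplies another home for the skin levels.

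**Step 3: extent.** Cohort 1 has up to 8 subjects. The schedule in Table 2 marks seven optional biopsy time points. Assuming one sample per time point, the ceiling is 8 × 7 = 56 values. The actual number is unknown because biopsy is optional. Cohort 2 has no biopsies. Photography concerns up to 8 + 12 = 20 subjects.

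**The case against.** Sections 4.10.4 and 4.10.5 define what enters the clinical database and what this SAP tabulates. They do not say that the measurements are not made. Section 3.1.19 says the samples are for measuring SYNT001, and Section 1 leaves room for additional analyses. A separate laboratory report, or a provision in the protocol, could deliver the result. The SAP is also open about the exclusion.

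This objection rules out several stronger readings:
- A reader might infer that the skin objective cannot be answered for any subject. The SAP does not support that, because data outside the database may still be generated and reported.
- For the same reason, it cannot be said that subjects undergo biopsy for a measurement that will never be reported.
- A reader might infer that 4.10.4 keeps the promised photographic assessment out of the database. It excludes only quantitative data, and images can be presented descriptively without a summary table. Lesion activity is in any case scored by the PDAI and summarised by cohort and visit under Section 4.9.4.
- The layout by dose and visit belongs to the photography endpoint. Skin levels are promised only across time points.

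What the objection does not remove is the gap in 4.10.5. Permission to perform additional analyses is not a plan to report a stated endpoint, and the SAP names no separate report or data source. The conflict lies between two sections of the same document, and neither acknowledges it.

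**Conclusion.** The point holds for skin biopsy. The SAP states an exploratory endpoint of SYNT001 levels in skin and plans no output that shows a result for it. It affects one exploratory endpoint and at most 8 subjects with optional samples. Dose selection rests on total IgG and the PDAI total activity score and is untouched, as are all other primary and secondary endpoints.

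For photography the point is secondary: the word quantitative in 4.10.4 does not fit the endpoint in 2.3, and the SAP does not say how the qualitative assessment will be presented.

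The conclusion assumes that the SAP is the full statement of planned outputs. If the protocol or a laboratory plan already names where skin levels are reported, a cross-reference in 4.10.5 would be enough.

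**What to change.** **Section 4.10.5.** Bring in the laboratory's results as an external data set and list them. Suggested wording: *SYNT001 concentrations in skin will be received from the laboratory as an external data transfer and listed by subject, time point and skin type (lesional or non-lesional). No summary table will be produced.* With at most 8 subjects giving optional samples of mixed skin type, a listing suffices. If the levels will not be reported under this SAP, amend Section 2.3 to say so.

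**Section 4.10.4.** Correct the word quantitative. Then either state how the qualitative assessment is presented by dose, regimen and visit, or recast the photographs in Section 2.3 as supportive documentation. A new Investigator rating at each visit is not needed: it would be an added assessment that the SAP does not describe.

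**Cost.** One data transfer and one listing for biopsy, or a wording change if 2.3 is amended instead. If the photographs are recast as supportive documentation, that change is wording only. Both should be settled before the programming specifications are finalised, which Section 6 places before database lock.
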